## **Symptoms:**

- The Brief Pain Inventory is a widely used measurement tool for assessing pain severity and pain interference.
- The Pittsburgh Sleep Quality Index (PSQI) is a self-report scale consisting of 19 items that produce a global sleep quality score and the following seven component scores: sleep quality, sleep latency, sleep duration, habitual sleep efficiency, sleep disturbance, use of sleeping medications, and daytime dysfunction. The PSQI has established internal consistency and reliability in various clinical populations of women (Cronbach alphas 0.80 across groups).
- The Berlin Questionnaire for sleep obstructive apnea is a 10-item questionnaire well-known for its accuracy in predicting the presence of sleep apnea in patients. It has established sensitivity and specificity (Cronbach alphas 0.86 and 0.77, respectively, when polysomnography was used for confirmation).
- The Epworth Sleepiness Scale is an 8-item self-report measure which provides a measure of a general level of daytime sleepiness, or average sleep propensity in daily life. It is widely used for making this assessment.
- The Patient Health Questionnaire-15 (PHQ-15) is a 15 item scale that inquires about somatic symptoms or symptom clusters that account for more than 90% of the physical complaints reported in the outpatient setting and include 14 of the 15 most prevalent DSM-V somatization disorder somatic symptoms. It has demonstrated internal consistency and convergent validity with the BDI ( $r = 0.559$ ;  $p < 0.01$ ).

## **Social Functioning and Quality of Life:**

- The Veterans RAND 12 Item Health Survey (VR-12) is a 12-item instrument used to measure health related quality of life and will be administered at various time-points.
- The PROMIS® instruments use modern measurement theory to reliably and validly assess patient-reported outcomes (PROs) for clinical research and practice. The PROMIS ® short forms for social functioning will be used in the proposed study.

## **Sexual Orientation and Gender Identity (SOGI):**

- In the current study, we will expand data collection of demographic variables to include sexual orientation and gender identity based on current recommendations for inclusive research. Currently enrolled participants in the study will be asked to verbally consent to participate in a follow-up phone visit to complete a demographic survey lasting no more than 15 minutes. This follow-up survey will include pertinent demographic items including sexual orientation and gender identity. Research team members will review the electronic medical record of the enrolled participants to gather their most current phone number and address. Currently enrolled participants will then be contacted by phone. If the participants are unable to be reached by phone within 10 days of first contact, a letter will be sent to the last known address of the participant. This letter will provide information regarding the follow-up visit and how to complete the visit or opt-out of the visit. All future participants will complete the SOGI demographic survey as part of their initial visit and will not require an additional follow-up phone visit.

## **Dark Enhanced Startle Assessment (Atlanta Only)**

Dark enhanced startle response will be assessed using a paradigm in which acoustic startle (blink) response is assessed in darkness versus light conditions. Data will be collected by trained research staff using Biopac MP150 for Windows. The acquired data will be processed using Mindware software and then exported to Excel for analyses. Dark enhanced startle data will be collected at Baseline, 2-Weeks Post and 3-Months Post Treatment.

## **Heart Rate Variability Assessment**

In order to measure heart rate variability, we will utilize the Firstbeat Bodyguard-2 device which is a reliable R-R interval recording device for short and long-term measurements. The device is lightweight and user friendly. The device is attached directly to the skin with two chest electrodes and begins recording data automatically. Participants will wear the device for up to 48-hours. Data will be downloaded directly to Firstbeat

Analysis Server or SPORTS software for analysis. This data will be used to monitor changes in heartbeat due to stress.

### ***Cardiovascular Disease Assessment (CVD)***

In order to screen for CVD, a 12-lead ECG will be conducted at the Baseline and Time 3 Visits by trained study staff. Results will be interpreted by [name], a co-investigator and cardiologist at the Atlanta VAMC and will be analyzed to evaluate the relationship between heart health and PTSD diagnosis/severity. Additionally, there are some ECG markers that are autonomic in nature (QT interval) and TC-TSY could positively influence this measure.

### ***Polysomnogram (Atlanta Only)***

Participants with moderate to high risk scores on the Berlin questionnaire and the Epworth Sleepiness Scale will be given the option of participating in a sub-study which involves taking part in an overnight sleep study (polysomnogram) at the Atlanta VA Sleep Lab. This will yield information regarding the prevalence of OSA and other sleep disorders in this sample of women Veterans as well as an objective measure of sleep quality. Participants who consent will be asked to complete an overnight sleep study at any point during their participation in the study. A stand-alone consent and HIPAA form will be provided to eligible, interested participants.

### ***Immunological Measures (IL-6, IL-10, C-Reactive Protein)***

Trained study personnel, CSC phlebotomists and VA Lab phlebotomists will perform blood draws. Blood samples of 25mL will be obtained using EDTA-containing (purple top) tubes. Tubes will be spun in a centrifuge and plasma will be pipetted into cryovials which will be stored in a freezer located in a VA laboratory. Trained study personnel will be responsible for processing the samples, ensuring proper storage and sample tracking. Samples will be labeled with the subject identification number and visit number. No identifiers will be included in the sample label. Plasma levels of IL-6, IL-10, and C-Reactive Protein will be obtained at Baseline, 2-Weeks Post and 3-Months Post Treatment.

**Table 1: Study Flowchart and Data Collection Schedule**

	Pre-Screen Phase	Screening Visit a	Baseline/ Randomization Visit	Mid-Tx Visit	2-Week Post Treatment Visit	3-Month Follow-Up Visit	Crossover Intervention d or subsequent survey
		Time-0	Time-1	Time-2	Time-3	Time-4	
Phone Screening	X						
Chart Review/Med. Clearance	X	X					
Inclusion/Exclusion Review	X	X					
Informed Consent/HIPAA		X					
AEs/Con Meds/VA Groups Log		X	X	X	X	X	
Basic Demographics/Updates		X	X	X	X	X	X
DRRI-2 Combat Experiences		X					
Childhood Trauma Ques.		X					
Life Events Checklist		X					
MINI (for DSM-5)		X					
Berlin Questionnaire		X				X	
Epworth Sleepiness Scale		X				X	
RANDOMIZATION			X b				

Beck Depression Inventory			X	X	X	X	X
Difficulties in Emotion Regulation Scale			X	X	X	X	
Dissociative Experiences Scale			X	X	X	X	
Brief Pain Inventory			X	X	X	X	X
Pittsburgh Sleep Quality Index		X	X	X	X	X	X
Patient Health Questionnaire			X	X	X	X	
PROMIS Measures			X	X	X	X	
PROMIS Social Isolation							X
CAPS-5			X	X	X	X	
PTSD (PCL-5)							X
Chronic Pain Survey (BPI)							X
PTSD-Checklist-5		X	X	X	X	X	X
Intervention Tracking				X	X	X	X
VR-12			X	X	X	X	X
12-Lead ECG			X		X		
Dark-Enhanced Startle Session e			X		X	X	
Heart Rate Variability Measure			X		X	X	
Blood Draw/Processing			X		X	X	
Provide Compensation		X	X	X	X	X	
Offer alternate intervention							X
Polysomnogram (optional)		X c,e					

aGiven the nature of this study, the T-0 and T1 Visits may be combined into one visit

bRandomization will occur after all other Baseline/Randomization Visit procedures have been completed

cThe sub-study will be described at the screening visit and if interested, consent will be obtained for eligible participants. The PSG can be completed at any time during study participation

dIf the participant elects to do the crossover intervention, measures will be administered by phone or in-person at baseline, mid-treatment and at 2-weeks and 3-months post treatment

e Given the availability of equipment, this measure will only be conducted for participants in Atlanta

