## **Medical Outcomes**

- Adverse Events will be assessed at each time-point.
- Concomitant Medications will be assessed at the Baseline/Randomization Visit and any changes will be documented at follow-up visits.
- VA Group Engagement will be assessed at all timepoints to determine if the Veteran is engaged in other groups and if so, which groups and how frequently they attend.

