### **Chart Review**

Data will be extracted from the VA medical record including diagnoses, active medications, and reportable adverse events (if applicable). These data will be added to the VA REDCap database.

**Self-Report and Interview Data:** Self-report and interview data will be captured through pen and paper measures or through direct data entry into the VA REDCap (Research Electronic Data Capture) project database using a VA-approved tablet. REDCap is a secure, web-based application designed to support data capture for research studies. REDCap for VA is installed and accessible only behind the VA firewall and data is backed-up nightly and every 6 hours. In addition, VA REDCap provides data de-identification features and

restricts access to PHI at the user-level. Deidentified self-report and interview data will be securely exported from VA REDCap to Excel or SPSS and then uploaded to the VA password-protected research drive for analysis as needed. Periodically, deidentified self-report and interview data will be submitted to the study statistician for data analysis and review.

Additionally, demographic information, including identifiers (study ID), for each participant will be stored in the REDCap database that is password-protected and accessible only by approved members of the research team. The research suite is locked at all times with access granted only to authorized personnel. Data residing on VA desktop computers are routinely backed up on a secure, off-site server. Thus, all data are protected from loss and are stored devoid of all patient identifiers.

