### **Power Analysis**

Given the estimated final sample size of 104 (52 per group) after expected levels of attrition (50% attrition from 210), we will be powered at 80% to detect moderate effect sizes for any differences between the groups (two-group independent t-tests effect size (Cohen's d) of 0.555 and chi-square tests for differences in proportions between the two-groups effect size (Cohen's omega,  $\omega$ ) 0.274 and higher) as well as moderate-to-large effect sizes detected for differences between the groups over time (repeated measures group-by-time interaction effects: effect size of 0.28, Cohen's f) will be detected. Power analyses will be completed using PASS v.13.0.8.

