## **G. DATA AND SAFETY MONITORING PLAN**

### **Data and Safety Monitoring Plan (DSMP)**

**Safety Monitoring:** The PI or anyone else who has contact with study participants during study activities have the responsibility to monitor for any potential adverse events and protocol deviations. Any potential participant for an adverse event will be reported immediately via “warm transfers” per VA guidelines at respective site and PI, who will contact the participant and determine if additional intervention is needed to ensure participant safety. Study personnel will be trained on these procedures, including contacting VA Police, on-call Mental Health providers Veterans Crisis Line and/or local crisis lines. Protocol deviations will also be immediately reported to respective site PI who will ensure that adverse events deemed to be unanticipated problems and protocol deviations are properly reported to the IRB in a timely manner. Detailed written documentation will be kept for all adverse events that occur over the course of the study. PI will hold regular meetings with study staff where they will discuss adverse events and protocol deviations associated with this project and ways to reduce repeat occurrences. Research staff will examine all cumulative adverse events quarterly to determine if there are any systematic problems and to implement protocol corrections as needed after receiving IRB approval.

**Data Monitoring:** All information linking study data to PHI will be kept within VHA electronically in secure computer files stored behind firewalls requiring password access, or in hardcopy form in locked file cabinets in locked offices. All patient identifiers will be removed prior to analysis. All investigators and team members who will have access to the data will have received appropriate background checks as part of hiring and/or credentialing and will have completed Data Security Training within the prior 12 months.

Per VHA guidelines, data resulting from this study will be stored locally on VHA password-secure folders. Requests for data access will be considered and responded to within one month of the request and datasets will be made available electronically. Requests must be made in writing to the study PI and provide information on the purpose for accessing the data.

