### **AE and SAE Monitoring**

For the proposed study, participants will be monitored at each data collection point and as indicated by notification from the yoga/CPT teachers at each intervention session. Adverse events and serious adverse events will be assessed for relatedness to study participation and whether the event was anticipated or unanticipated. Those adverse events found to be unanticipated and related to study participation will be reported to IRB and VA R&D according to local reporting guidelines.

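### Active adverse-event ascertainment is scheduled only at study visits and through session notifications, and the plan does not say how or when events are found in women who stop attending

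*Combined protocol and SAP*

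**What the plan says.** All references are to the combined protocol and SAP.

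- **Active assessment.** Medical Outcomes: "Adverse Events will be assessed at each time-point". In Table 1 the row "AEs/Con Meds/VA Groups Log" is marked from Time 0 to Time 4. AE and SAE Monitoring: "participants will be monitored at each data collection point and as indicated by notification from the yoga/CPT teachers at each intervention session".
- **Duty of staff.** The Data and Safety Monitoring Plan does not leave monitoring to the PI alone: "anyone else who has contact with study participants during study activities have the responsibility to monitor for any potential adverse events and protocol deviations". It also has research staff look at cumulative events each quarter.
- **Medical record.** The Chart Review paragraph under Data Management: "Data will be extracted from the VA medical record including diagnoses, active medications, and reportable adverse events (if applicable"). It gives no date, frequency or population for this extraction.
- **Chart review schedule.** Table 1 marks "Chart Review/Med. Clearance" at pre-screen and at the screening visit, and nowhere later.
- **The commitment.** Data and Safety Monitoring Plan: "Detailed written documentation will be kept for all adverse events that occur over the course of the study".
- **Expected loss.** Power Analysis: 104 women (52 per group) remain "after expected levels of attrition (50% attrition from 210"). Data Quality counts a woman as retained only if she completes every assessment.

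The Informed Consent Process lets a woman withdraw at any time. No section describes a safety contact, closing call or record check for a woman who stops attending.

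**The concern.** Harm is a plausible reason for leaving. The protocol's own risk section expects some distress in both arms and names physical risks of yoga. If adverse events are asked about in full among women who attend, but looked for less often and less widely among women who leave, the safety record leans towards those who tolerated treatment. If leaving differs between arms, the between-arm comparison of harms can be distorted as well. A hospitalisation, emergency visit or crisis contact in a woman who left could sit in the VA record unread. The quarterly review cannot correct this, because it sees only events already captured. Data Quality examines attrition and missing data in general terms, but nothing is written about incomplete safety data.

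**Working it through.** **1. Routes by which an event can reach the study after randomization**

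| Route | Section | Scope | Works if she stops attending? |
|---|---|---|---|
| Assessment at time-points | Medical Outcomes; Table 1 | All adverse events | Only if the assessment still takes place |
| Notification by group leaders | AE and SAE Monitoring | What is noticed at a session | No |
| Staff in contact during study activities | Data and Safety Monitoring Plan | Any potential event | Only if there is contact |
| Participant reports new onset | Safety Assessments | Listed symptoms | Only if she reports |
| Weekly reminder calls | Both intervention sections | Attendance; no adverse-event question stated | Not stated |
| VA record extraction | Chart Review | Reportable events; no timing | Yes, if it is done |

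Only the last route is independent of her attendance or her own report. It is also the only one with no schedule, and its scope is narrower than the assessment of women who attend. AE and SAE Monitoring sends to the IRB those events that are unanticipated and related to participation. If reportable has that meaning in the Chart Review paragraph, anticipated or unrelated events in the record are outside the extraction.

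**2. The plan's attrition figure**

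210 × (1 − 0.50) = 105, against 104 stated. The implied attrition is 1 − 104/210 = 50.5%. The figure reproduces apart from rounding, and 104/2 = 52 per group.

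**3. Worst-case precision**

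Assumptions: equal allocation, so 210/2 = 105 per arm; all 210 randomised; every non-completer gives no adverse-event data. With zero events seen in n women, the one-sided 95% upper bound on the rate is 1 − 0.05^(1/n).

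- n = 52 per arm: 1 − 0.05^(1/52) = 5.6%
- n = 105 per arm: 1 − 0.05^(1/105) = 2.8%
- Both arms pooled: 2.8% with 104, 1.4% with 210

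A milder case, also assumed: if half of the non-completers gave full data, about 78 per arm would be covered, and 1 − 0.05^(1/78) = 3.8%.

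**4. Worst-case capture**

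The bounds in step 3 show lost precision, not bias. For bias, suppose that women who leave have r times the risk of those who stay, and that none of their events is found. With 104 staying and 106 leaving, the share of affected women captured is 104/(104 + 106r):

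- r = 1: 104/210 = 50%
- r = 2: 104/316 = 33%
- r = 3: 104/422 = 25%

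The documents give no value for r; these are illustrations.

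**The case against.** A reader might infer that adverse events are sought only at attended visits and sessions, and that women who leave fall out of safety follow-up altogether. The documents do not support that.

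- The Chart Review paragraph names the VA record as a source, and the Data and Safety Monitoring Plan adds a duty that arises from any contact during study activities. The COVID-19 Contingency Plan allows remote or telephone assessment, so missing an in-person visit need not mean missing data.
- The Table 1 row sits between phone screening and the inclusion/exclusion review and reads most naturally as an eligibility step. It is not a full schedule of record access: sleep-study results are also taken from the record, and staff consult it for the contact details of enrolled women. The row therefore does not show that record review stops at screening.
- Reportable may describe the class of event sought rather than events already known to staff.
- The 50% is not a count of women lost to safety follow-up. Missing one assessment makes a woman not retained, and no section says that stopping sessions ends visits. Power Analysis does not say that the 210 are randomised.
- The consent pages were removed before review, so what they allow after a woman stops cannot be checked here.

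All of this stands, and it limits the point. It does not remove it. Even if the record extraction is meant to be continuous, it is written for reportable events only and with no dates, while women who attend are assessed for all events.

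**Conclusion.** The point holds as a gap in planned ascertainment and as a need to reconcile the Chart Review paragraph with Table 1. Women who stop attending are covered at most by an unscheduled search for reportable events. That falls short of the commitment to document all adverse events, and it may understate harms in a trial that plans for 50% attrition.

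The size is uncertain. The contrast of 5.6% with 2.8% per arm is a worst case that needs every non-completer to give no adverse-event data and all 210 to be randomised. The true loss is probably smaller. Distortion between arms is a possibility only, since no attrition by arm is given. This should be changed, because the remedy is concrete and cheap.

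**What to change.** 1. In Table 1, add a separate row for an adverse-event chart check at the scheduled dates of Times 2, 3 and 4. Apply it to every randomised woman whose consent and HIPAA authorization still allow record review, whether or not she attends. The post hoc equivalence section shows that analysis has already taken place, so where those dates have passed, do the check retrospectively.
2. In the Chart Review paragraph, replace the restriction to reportable events with all recorded adverse events since the last check, including hospitalisations, emergency visits and crisis contacts, and refer to the new Table 1 row for timing.
3. Report adverse events by arm with all randomised women as the denominator, and state for each arm how many had chart-only follow-up.

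The cost is protocol wording and modest staff time, using a record source the study already draws on. Three limits remain: care outside the VA will be missed, chart-only data are less complete than interview data, and the consent and HIPAA wording must be confirmed to cover record review after visits stop.

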### **Informed Consent Process**

Informed consent in Atlanta will be obtained by trained staff during the Screening/Consent Visit in a private room at the AVAMC Clinical Studies Center or the Trauma Recovery Program located at the Henderson Mill Annex. In Portland, informed consent will be obtained by trained staff during the Screening/Consent Visit in a private room at the VA Portland Health Care System at either the Portland or Vancouver VA Medical Center. Participants will be informed that they are being asked to participate in a research study. They will be told the nature of the procedures and the interventions, informed of the risks associated with their participation, asked to read the consent form, and encouraged to ask questions or discuss any pertinent issues. They will be told that declining to participate will not influence or compromise their care or employment at the either VAMC (if pertinent). Participants will be notified that the research project is voluntary, that participation can be stopped at any time and that participation will not impact any services or benefits they receive at the Atlanta or Portland VAMC. Participants will also be informed that they will be compensated for time and travel. All research volunteers will be asked to sign the consent form after they have read it and discussed the study with research personnel. Participants will be given as much time as needed to read the form thoroughly and have all questions addressed. Study personnel will ask questions to determine adequate comprehension of the study. Only participants who have given their written informed consent will participate. In addition to informed

consent, subjects will read and sign a HIPAA authorization. Participants may withdraw their consent at any time and may withdraw from the study at any time.

